# 6.2 Subject Exclusion Criteria

- Previous radiotherapy to the intended treatment site that precludes developing a treatment plan that respects normal tissue tolerances.
- Serious medical co-morbidities precluding radiotherapy.
- Pregnant or lactating women.
- Target lesion(s) is/are complicated bone metastases that include clinical or radiological evidence of spinal cord compression or impending pathological fracture.
- Leptomeningeal disease.
- Malignant pleural effusion.
- Absolute neutrophil count (ANC) <1.0 K/mcL and platelet count <50 K/mcL at time of enrollment.
- Patients whose entry to the trial will cause unacceptable clinical delays in their planned management.

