# 8.0 PRETREATMENT EVALUATION

The following tests must be completed prior to enrollment unless otherwise specified:

Prior to study entry (randomization):

patients approached (if applicable).

• Standard of care biopsy proving malignancy, with clinical documentation consistent with metastatic disease, per physician discretion.

Within 6 weeks (42 days) of study entry (randomization):

- CT CAP, FDG-PET/CT scan, MRI Total Spine or NaF-PET can be used, imaging study is at the discretion of the treating physician.
- Other local imaging studies that include the target lesion(s) can also be used as baseline imaging at the discretion of the treating physician.

Within 4 weeks (28 days) of study entry (randomization):

- CBC with differential
- Comprehensive metabolic panel (CMP=Na, K, Cl, CO2, BUN, Creatine, Ca, Glucose, total protein, albumin, alk phos, total bilirubin, AST and ALT).
- Complete medical history including current medications, comorbidities and performance status
- Physical exam including weight, height and vital signs (O2 saturation, blood pressure, heart rate, respiratory rate, and temperature).
- BPI short form and EQ-5D-5L
- Lesion Identification Worksheet should be completed by physicians

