#### 9.0 TREATMENT/INTERVENTION PLAN

Patients who have metastatic cancer and greater than 5 sites of disease will be enrolled. Patients may also have newly diagnosed stage IV disease. Patient will be randomized to standard of care therapy or to receive RT to selective bone metastases prior to continuation of standard therapy.

9.1 RT

Page **14** of **30** Version: 2/26/16

Patients will undergo RT to each lesion using one of the dose and fractionation regimens in the table below. Accounting for the patient"s global clinical status, the treating radiation oncologist should select a RT regimen that would result in optimal lesion local control while not exceeding local normal tissue radiation tolerance:

Page **15** of **30** Version: 2/26/16

Total Dose	Fractions	Dose per Fraction	Verification Imaging
2000cGy	5	400cGy	MV or KV
3000cGy	10	300cGy	MV or KV
3000cGy	5	600cGy	KV and CBCT
3500cGy	5	700cGy	KV and CBCT
2400cGY	3	800cGy	KV and CBCT
2700cGy	3	900cGy	KV and CBCT
2400cGy	1	2400cGy	KV and CBCT

Patients will first be simulated using appropriate immobilization as determined by the treating radiation oncologist. This will be followed by acquisition of a CT scan in the treatment position. The use of intravenous or oral contrast will be at the discretion of the treating radiation oncologist. Dose constraints will be followed according to department standards and will depend on the radiation technique and total dose prescribed.

The treating radiation oncologist must delineate the gross tumor volume (GTV). Clinical target volume (CTV) will be defined as the GTV plus a margin required for microscopic extension of tumor. The planning target volume (PTV) should expand the CTV by an amount necessary to account for uncertainty in patient positioning and treatment delivery.

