#### 13.0 CRITERIA FOR REMOVAL FROM STUDY

Patients will be removed from the study if any of the following criteria are met, after review by the principal investigator:

- 1. A change in the patient's medical status unrelated to RT results in the patient being unable to comply with the protocol.
- 2. Patient is unable to continue follow-up as outlined within the protocol
- 3. Patient is found to be ineligible based on the criteria in section 6.0 of this protocol.
- 4. Patient requests to withdraw from the protocol.
- 5. Patient death.

Otherwise, patients will continue on protocol until 12 months have elapsed since date of randomization or until an SRE occurs.

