#### 15.2 Randomization

Patients will be randomized to the standard of care therapy arm or the early, upfront RT followed by standard of care therapy arm. For patients enrolled, immediately after consent is obtained, the CRC at MSKCC will register participants in the Clinical Trial Management System (CTMS). Once the participant's eligibility is established, the registration will be finalized and the participants will be randomized using the Clinical Research Database (CRDB). Randomization will be accomplished by the method of random permuted block, and will be stratified by disease histology and planned standard of care. After

Page **23** of **30** Version: 2/26/16

treatment arm is determined by randomization, the CRCs will notify physicians at MSKCC of the treatment arm within 24 hours of randomization. All data will be collected and analyzed at MSKCC.

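### Randomised patients can be removed as ineligible on findings made after randomisation, and RT planning makes such findings more likely in Arm 2 than in Arm 1

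*Combined protocol and SAP*

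**What the plan says.** Section 13 opens: "Patients will be removed from the study if any of the following criteria are met, after review by the principal investigator". The third criterion is that the "Patient is found to be ineligible based on the criteria in section 6.0 of this protocol". It gives no cut-off date, no limit on the source of the information and no masking of the review. It does not mention arm.

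Two Section 6.2 exclusions bear on this:

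- "Previous radiotherapy to the intended treatment site that precludes developing a treatment plan that respects normal tissue tolerances"
- "Target lesion(s) is/are complicated bone metastases that include clinical or radiological evidence of spinal cord compression or impending pathological fracture"

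Before randomisation, both arms have imaging within 42 days (Section 8.0: "CT CAP, FDG-PET/CT scan, MRI Total Spine or NaF-PET can be used, imaging study is at the discretion of the treating physician"), and history and examination within 28 days. Sections 15.1 and 15.2 require eligibility to be confirmed before randomisation, and Section 16.2 has the principal investigator verify each case at enrolment. Section 4.1 has up to five target lesions documented at randomisation in both arms.

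Simulation, the planning CT ("This will be followed by acquisition of a CT scan in the treatment position") and target delineation are described in Section 9.1, which covers RT and so applies only to Arm 2. The first scheduled visit common to both arms after randomisation is at 3 months, with imaging at the physician's discretion (Section 10.0).

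Section 14.0 states that the primary analysis is not intent-to-treat, requires a valid SRE endpoint, and leaves out patients who withdraw before that endpoint can be evaluated. It does not say how patients removed as ineligible are handled.

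**The concern.** An exclusion after randomisation is harmless to the comparison only if its chance does not depend on the assigned arm. Here it can. Whether earlier radiotherapy prevents an acceptable plan is a planning result: the history shows that radiotherapy was given, but the question is fully answered only by attempting a plan. Only Arm 2 has that step on schedule, together with an additional CT on which the treating radiation oncologist delineates each treated lesion. Two patients alike at baseline therefore have different chances of being found ineligible afterwards, under a rule with no time limit and in an open-label trial.

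If removed patients then leave the primary analysis, the analysed arms are no longer the randomised arms. With 37 patients per arm, a few removals of patients whose SRE risk differs from the average would shift the comparison.

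**Working it through.** **1. The plan's own figures.** Inputs from Section 14.0: 60% versus 30% SRE, one-sided alpha 0.05, power above 80%, 1:1 allocation.

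n per arm = [1.645·√(2·0.45·0.55) + 0.842·√(0.60·0.40 + 0.30·0.70)]² / 0.30² = 32.9, so 33 per arm and 66 in total. Over-accrual: 66/(1 − 0.10) = 73.3, so 74. Both stated figures reproduce. The allowance is 74 − 66 = 8 patients, or 4 per arm.

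**2. Who is looked at, and when.**

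| Step | Arm 1 | Arm 2 |
|---|---|---|
| Baseline imaging, history, eligibility check | Yes | Yes |
| Simulation, planning CT, target delineation after randomisation | Not scheduled | Scheduled |
| Test of whether a tolerable plan exists | Not scheduled | Occurs when planned |
| Visits at 3, 6 and 12 months, imaging discretionary | Yes | Yes |

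The arms differ only in the second and third rows, and the third is the subject of one exclusion criterion.

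**3. Possible size.** Assumptions, not document figures: one lesion per patient, 37 per arm, no RT effect (60% SRE in both arms, the plan's control rate), m Arm 2 patients removed whose SRE risk is q, none removed from Arm 1, and removed patients not analysed.

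SRE rate among Arm 2 patients left = (37·0.60 − m·q)/(37 − m).

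For m = 3:

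- q = 1.0: (22.2 − 3.0)/34 = 56.5%
- q = 0.8: (22.2 − 2.4)/34 = 58.2%
- q = 0.6: (22.2 − 1.8)/34 = 60.0%
- q = 0.3: (22.2 − 0.9)/34 = 62.6%

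Test: z = (p₁ − p₂)/√[p̄(1 − p̄)(1/37 + 1/(37 − m))], with p₁ and p₂ the observed proportions and p̄ the pooled one; reject if z > 1.645. The rejection probability is summed exactly over the two binomial distributions:

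| Removed from Arm 2 | q = 30% | q = 60% | q = 80% | q = 100% |
|---|---|---|---|---|
| 2 | 3.7% | 4.9% | 6.0% | 7.2% |
| 3 | 3.2% | 5.2% | 7.0% | 9.2% |
| 4 | 2.2% | 4.5% | 7.0% | 10.3% |

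With no removals the figure is 5.4%; it differs from 5% because the test statistic is discrete. Four removals use up one arm's share of the over-accrual.

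**4. Effect of keeping everyone.** With all 74 analysed (37 per arm), the same exact method gives power of about 0.84 at 60% versus 30%, if every outcome is known and the effect is undiluted. No larger sample is needed.

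**The case against.** The strongest reply is that the safeguards come before randomisation. Both arms are imaged, eligibility must be established first, the principal investigator checks each case, and the target lesions are already listed. Criterion 3 is worded identically for both arms, and nothing says that eligibility is judged again on the planning CT. All of this is accurate. It lowers the number of late findings but does not close the rule, which still permits removal on anything learned later.

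Four stronger readings are tempting and are not supported:

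- *Only Arm 2 can lose patients this way.* Arm 1 has history and examination at follow-up, with imaging at discretion, and can also be found ineligible. The difference is in the chance of detection.
- *Only planning reveals these exclusions.* Cord compression and impending fracture are clinical or radiological findings that baseline imaging can show in either arm. Only the prior-RT criterion depends on planning, and records inform that one too.
- *The worst lesions are dropped from the RT arm.* The rule removes patients, not lesions, and the documents do not say that a previously irradiated site carries a higher SRE risk.
- *The bias favours RT.* It would if those removed had above-average risk, as is plausible for early cord or cortical compromise. But SREs count from randomisation and cord compression is itself an SRE, so a compression found at planning could instead be scored against RT. The documents do not settle this.

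It can also be said that removal from study is not the same as exclusion from analysis: death is a removal criterion too, yet the analysis window runs to death. That stands. Loss from the primary analysis is an inference from the non-intent-to-treat wording and the need for a valid endpoint. Analysing all randomised patients as assigned would resolve most of the problem, provided it expressly covers patients later judged ineligible.

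**Conclusion.** The concern holds as one of unequal detection. As written, the plan allows exclusion after randomisation on information that the protocol schedules only in Arm 2, without masked review and with a primary analysis that does not commit to keeping such patients. That can make the analysed arms non-comparable.

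The documents fix neither the sign nor the size. In the illustration with three removals, type I error runs from 3.2% to 9.2% according to the risk of those removed. Average-risk removals cause no inflation. The number removed, their risk, the absence of Arm 1 removals and one lesion per patient are all assumed. The threat is modest, and it is worth correcting because the correction is cheap.

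**What to change.** 1. **Section 13, criterion 3:** exclude a randomised patient for ineligibility only if the ineligibility was present on information dated before randomisation, applied identically in both arms. Preferably, someone unaware of the allocation makes that judgement.
2. **Section 6.2 and the eligibility checklist:** judge the prior-RT and complicated-lesion criteria for all listed target lesions before randomisation, from existing records and baseline imaging.
3. **Section 14.0:** state that a patient with a later planning finding stays in follow-up and in the primary analysis in the assigned arm, whatever treatment is given.
4. **Reporting:** tabulate removals by arm and reason.

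The cost is wording in these sections, a line on the checklist and a little review time before randomisation; a masked judgement adds a small task when a case arises. No patients or study visits are added. The statistical downside is slight dilution from Arm 2 patients who do not receive protocol RT.

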#### 4.0 OVERVIEW OF STUDY DESIGN/INTERVENTION

# 4.1 Design

This is a randomized (1:1) single institution trial in patients with metastatic solid tumors. Subjects will be randomized to receive either standard of care or upfront, early RT to high risk bone followed by standard of care therapy at the discretion of the treating medical oncologist. At the time of randomization, physicians will fill out the Lesions Identification Worksheet (Appendix) to document the ≤5 highest risk bone metastases per protocol definition to be followed during the protocol in both arms.

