# 6.1 Subject Inclusion Criteria

- Histologically confirmed solid tumor malignancy with greater than 5 sites of metastatic disease detected on imaging.
- Has high risk bone metastases that are asymptomatic or minimally symptomatic (not requiring opioids). High risks metastases are defined as: 1. bulkiest sites of osseous disease ≥ 2cm, 2. disease involving the hip (acetabulum, femoral head, femoral neck),

Page **12** of **30** Version: 2/26/16

shoulder (acromion, glenoid, humeral head), or sacroiliac joints 3. disease in long bones with1/3-2/3 cortical thickness (humerus, radius, ulna, clavicle, femur, tibia, fibula, metacarpus, phalanges) 4. disease in junctional spine (C7-T1, T12-L1, L5-S1) and/or disease with posterior element involvement.

- ECOG performance status 0 − 2.
- Age ≥ 18 years.
- Able to provide informed consent.
- Patients at reproductive potential must agree to practice an effective contraceptive method. Women of childbearing potential must not be pregnant or lactating.

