## 10.0 EVALUATION DURING TREATMENT/INTERVENTION

All patients in Arm 2 (RT arm) will be assessed for toxicities according to CTCAE v 4.0 and pain score using BPI short form once every 5 treatment days. Only patients in Arm 2 (RT arm) will have radiation treatment related adverse event evaluation. Following randomization, all patients in Arm 1 and Arm 2 will be scheduled for follow-up at 3 months (+/- 4 weeks), 6 months (+/- 4 weeks), 12 months (+/- 4 weeks), and receive the following assessments:

- CBC with differential
- Imaging studies (Follow-up imaging at the discretion of the treating physicians)
- History and physical
- Performance status
- Adverse event evaluation (CTCAE V 4.0) (Excluding Arm 1 patients)
- BPI Short Form
- EQ-5D-5L

•

In the event of an SRE, the following assessments should be completed within one week. As it may not be feasible that the research team will be notified of all SREs within one week, or a patient may not be able to come to MSK, these assessments are optional, but highly recommended:

- CBC with differential
- Imaging studies (Follow-up imaging at the discretion of the treating physician)
- History and physical
- Performance status
- Adverse event evaluation (CTCAE v 4.0)
- BPI Short Form
- EQ-5D-5L

If patient is unable to come in for a follow-up appointment or within one week of an SRE occurring, a telephone follow-up will suffice. The CBC with differential, history and physical, performance status and imaging studies will be deferred. If the patient has had any of these assessments completed locally, records should be obtained to fulfill these requirements. If the attending physician is able, the adverse event evaluation can be completed over the phone.

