## 14.0 BIOSTATISTICS

The primary objective of this study is to compare the rate of skeletal related events (SRE) from the date of randomization to death or 12 months, whichever occurs first, between patients who received standard of care versus upfront, early palliative RT to high-risk bone metastases. We expect 60-80% of the enrolled patients can be followed for 1 year. An SRE is defined as pathological fractures, spinal cord compression, or palliative radiotherapy and orthopedic surgery for bone pain. Data suggest that the event rate is around 60% in the standard of care arm . In our institutional experience, 75% of inpatient radiation consultation led to palliative radiation for painful bone

metastasis, an SRE. Furthermore, 61% of these lesions were diagnosed at least 4 months prior to undergoing RT. We believe 60% estimated event rate at 1-year is a conservative estimate.

The primary endpoint is a binary variable and the rate refers to proportion and is defined as the number of lesions that had SRE divided by the total number of target lesions. This analysis is lesion-based so an SRE (or no SRE) at one site does not affect the status of other sites from the same patient. We estimate that the investigational arm has the event rate around 30%. Radiation therapy is extremely effective in alleviating pain due to bone metastases with 70-80% pain control. By preventing the development of significant bone pain, which often leads to SREs, RT can effectively reduce SREs, To this end we will analyze at least 66 patients with valid SRE endpoint (randomized 1:1 to each arm) to achieve >80% power in detecting such a difference using a two-sample, one-sided proportion test with alpha<0.05. Since patients who withdraw before the endpoint can be evaluated will not be included in the analysis (i.e., it will NOT be an intent-to-treat analysis) we will over-accrue to account for withdrawals to ensure a minimum of 33 patients in each arm (subject to stratification, see Section 15.2) who can contribute the analyzable endpoint of SRE. We believe an additional 10% would be sufficient so totally we expect to randomize 74 patients. A small portion of patients (<15%) may have multiple lesions, in which case they will be treated as independent analysis units. In other words, the eventual effect sample size may be slightly higher than 66 because this objective will be analyzed per lesion.

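### Section 13 ends time on protocol at an SRE, but the Section 14 primary endpoint needs every target lesion followed to death or 12 months

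*Combined protocol and SAP*

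**What the plan says.** Section 13.0 (Criteria for Removal from Study) lists five numbered reasons for removal. An SRE is not one of them. The section then ends: "Otherwise, patients will continue on protocol until 12 months have elapsed since date of randomization or until an SRE occurs". The SRE in that sentence is not limited to a target lesion.

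Other sections assume that follow-up goes on after an SRE:

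- Section 14.0 sets the primary window from randomization to death or 12 months. It defines the rate as "the number of lesions that had SRE divided by the total number of target lesions" and adds that "an SRE (or no SRE) at one site does not affect the status of other sites from the same patient".
- Section 4.1 has physicians record up to five "highest risk bone metastases per protocol definition to be followed during the protocol in both arms".
- Section 10.0 says that "all patients in Arm 1 and Arm 2 will be scheduled for follow-up at 3 months", and again at 6 and 12 months, with no exception after an SRE.
- Section 12.2 counts the number and duration of hospitalizations for SREs in both arms.
- Section 14.0 uses the same death-or-12-months window for secondary endpoints unless stated otherwise, and lets pain-free and overall survival run past 12 months.

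On incomplete follow-up, Section 14.0 says only that "patients who withdraw before the endpoint can be evaluated will not be included in the analysis". On lesion numbers it says: "A small portion of patients (<15%) may have multiple lesions".

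**The concern.** The plan gives two different end points for collecting primary-endpoint data. A lesion-level proportion in which each site keeps its own status requires the remaining sites to be watched after one of them has an event. Section 13, read literally, stops that.

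The trigger for leaving is the primary event itself. Exit would therefore depend on outcome and, if the treatment works as assumed, would differ by arm. Three things are at stake:

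- **Target lesions in multi-lesion patients.** Second and later lesion events are lost, more of them in the control arm.
- **Single-lesion patients.** An SRE at an untracked site would end follow-up of a target lesion that has had no event. Section 6.1 requires "Histologically confirmed solid tumor malignancy with greater than 5 sites of metastatic disease detected on imaging", so disease outside the target lesions is expected, though those sites need not be in bone.
- **Secondary endpoints.** SRE hospitalizations, later BPI and EQ-5D-5L scores, and pain-free and overall survival would be cut at the first SRE, unless the Section 10 schedule and the Section 14 windows are taken to override Section 13.

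**Working it through.** **1. The plan's own figure.** Inputs from Section 14: 60% and 30%, one-sided alpha 0.05, power above 80%, 33 analysable patients per arm. A two-proportion test with pooled variance under the null and no continuity correction gives 33 per arm and power 80.06%. Then 66/(1 − 0.10) = 73.3, rounded up to 74 randomized. The design reproduces, and it presupposes follow-up to death or 12 months.

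**2. A check against the plan's expected follow-up.** Section 14 expects 60–80% of patients to be followable for 1 year. With one lesion each, exit at an SRE alone would leave 40% of controls and 70% of the RT arm at 12 months. That averages (40 + 70)/2 = 55%, before any death or withdrawal.

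**3. Several lesions, all kept in the denominator.** Let a share f of patients have k lesions, with lesion risk p = 0.6 or 0.3. Assumptions: lesions independent (as Section 14 treats them), no deaths, at most one lesion event recorded per patient, unfollowed lesions counted as event-free.

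Observed rate = [(1 − f)p + f(1 − (1 − p)^k)] / [(1 − f) + fk]

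For f = 0.15 and k = 2:

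- Control: (0.85 × 0.6 + 0.15 × 0.84)/1.15 = 0.636/1.15 = 55.3%
- RT: (0.85 × 0.3 + 0.15 × 0.51)/1.15 = 0.3315/1.15 = 28.8%
- Lesions per arm: 33 × 1.15 = 37.95
- Events missed per 33 patients, 33 × 0.15 × p²: 1.78 control, 0.45 RT

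| Share f | Lesions k | Difference (points) | Power, exit at first SRE | Power, full follow-up |
|---|---|---|---|---|
| 0 | 1 | 30.0 | 80.1% | 80.1% |
| 5% | 2 | 28.7 | 78.7% | 81.8% |
| 15% | 2 | 26.5 | 76.4% | 84.8% |
| 15% | 3 | 22.8 | 70.6% | 88.6% |
| 15% | 5 | 17.4 | 60.7% | 93.6% |

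Full-follow-up power rises with k because the plan counts each lesion as an independent unit.

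Some paired events would be recorded together, for example in one RT course. Adding f·s·p² to the numerator for f = 0.15, k = 2 gives 27.4 points (79% power) when s = one quarter, and 28.2 points (81%) when s = one half.

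**4. Several lesions, unfollowed ones dropped.** The denominator becomes (1 − f) + f[(1 − (1 − p)^k) + k(1 − p)^k]. For f = 0.15 and k = 2:

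- Control: 0.636/1.024 = 62.1%
- RT: 0.3315/1.0735 = 30.9%
- Difference: 31.2 points

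The direction of the error reverses.

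**5. Single-lesion patients with a non-target SRE.** The plan gives no risk q for this, so q is assumed, equal in both arms. With constant hazards h = −ln(1 − p) and g = −ln(1 − q):

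Observed rate = h/(h + g) × [1 − exp(−(h + g))]

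| q | Difference (points) | Power, 33 per arm |
|---|---|---|
| 5% | 29.4 | 78.8% |
| 10% | 28.8 | 77% |
| 20% | 27.6 | 75% |
| 30% | 26.3 | 72% |
| 40% | 24.9 | 68% |

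**6. Questionnaires.** With one lesion and constant hazard, the share gone by month t is 1 − (1 − p)^(t/12). That is 20.5% of controls and 8.5% of the RT arm by month 3, and 36.8% and 16.3% by month 6. Later between-arm comparisons would be made in unequally selected groups.

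**The case against.** The best case against is that this is one stray clause. An SRE is not among the numbered removal criteria, remaining on protocol is never defined, and Sections 4.1, 10, 12.2 and 14 all point to continued follow-up. Every figure above depends on staff obeying the outlying sentence, and nothing in the document shows that they do. Section 10 also provides for assessments within a week of an SRE, by telephone if needed.

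On size, the plan expects fewer than 15% of patients to have more than one lesion. For a single-lesion patient, stopping at that lesion's own SRE does not alter its binary outcome. The 84.8% comparator is not claimed by the plan; against its more-than-80% target the two-lesion shortfall is about 4 points, and it vanishes if half of paired events are recorded together. The non-target risk has no source in the document. With the Section 14 denominator the bias runs toward no difference, and dropping lesions extends to single lesions a rule that Section 14 states only for patients who withdraw.

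Much of this stands as a limit on size. It does not remove the contradiction. The sentence sits under removal from study, the one-week assessments are optional and do not replace follow-up of the other lesions to month 12, and no text says which section prevails.

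**Conclusion.** The concern holds. Section 13 and Section 14 give incompatible rules for how long primary-endpoint data are collected, and the other follow-up provisions side with Section 14. The sample size is not in error.

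The consequence is conditional on a literal reading of Section 13. With two independent lesions in 15% of patients, the expected difference falls by 3.5 points and power is 76.4%. The effect is smaller if fewer patients have several lesions or if paired events are recorded together, and larger if multi-lesion patients have three to five lesions. It reverses sign if unfollowed lesions are dropped. Single-lesion patients are affected only through SREs at non-target sites, at a risk that has to be assumed.

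The conclusion rests on the conflict between the sections, not on any one scenario. It must be fixed, because the clause governs who is observed for the primary endpoint, and data not collected after an SRE, questionnaires above all, may not be recoverable.

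**What to change.** 1. In Section 13, delete the clause that ends time on protocol at an SRE.
2. State there that all randomized patients, whatever SREs occur and at whatever site, stay in follow-up until death, withdrawal of consent or 12 months. This covers SREs at every worksheet lesion, SRE hospitalizations, start of opioids, survival, and the BPI and EQ-5D-5L.
3. In Section 14, state how a target lesion not followed to death or 12 months is counted.

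The cost of these is low: one clause removed, a few sentences added, and some data collection after an SRE through the visits and the telephone and records route already in Section 10. The stated numbers (33 per arm, 66 analysable, 74 randomized) do not change.

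Separately, reconcile the 12-month end of follow-up in Section 13 with the Section 14 statement that pain-free and overall survival may run beyond 12 months. That conflict remains after the clause is deleted. It is a larger change, needing either longer follow-up or a changed endpoint window.
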